6.7 CONCOMITANT MEDICATION

All treatments received by the patient during the “on-treatment” period of the trial must be documented in the CRF.

6.7.1 Allowed Medications/Treatments

- Therapies for pre-existing and treatment-emergent medical conditions, including pain management.
- Blood products and transfusions, as clinically indicated.
- Bisphosphonates.

- In case of nausea or vomiting, extended symptomatic treatment for emesis will be allowed.
- CSFs or erythropoietin treatment according to the American Society of Clinical Oncology (ASCO) guidelines.
- Anticoagulants.

6.7.2 Prohibited Medications/Therapies

- Concomitant administration of any antineoplastic therapy (other than those specifically allowed).
- Any radiotherapy other than limited field irradiation for cancer pain control exclusively.
- Immunosuppressive therapies other than corticosteroids for antiemetic prophylaxis and/or pain control.
- Aprepitant and equivalent agents (e.g., fosaprepitant) for patients allocated to the PM01183 arm (Arm A).
- Primary CSF prophylaxis for patients allocated to the PM01183 arm (Arm A), unless recommended by the IDMC after the interim safety analysis.
- Any other investigational agent/s.

6.7.3 Drug-drug Interactions

In vitro studies using human liver microsomes have shown that PM01183 has the potential to inhibit cytochrome CYP2B6, CYP2C8 and CYP3A4. Moreover, the K_i values compared with the achieved maximum plasma concentration (C_{max}) values at relevant doses indicate that the likelihood of a clinically relevant inhibition of PM01183 is possible for CYP2B6 and CYP2C8 ($[I]/K_i > 0.1$) and likely for CYP3A4 ($[I]/K_i > 1$). Additional *in vitro* studies have demonstrated no time dependent inhibition or irreversible inhibition for cytochrome CYP3A4. The magnitude of the interaction is unknown at present. Therefore, caution should be exercised when PM01183 is administered concomitantly with CYP2B6, CYP2C8 and CYP3A4 substrates.

Additionally, *in vitro* studies with human microsomes have shown that CYP3A4 is the major CYP isoform involved in the metabolism of PM01183, followed by CYP2E1, CYP2D6 and CYP2C9. The estimated contribution of the other CYP isoenzymes to the PM01183 metabolism is considered to be negligible. Therefore, concomitant drugs which induce or inhibit any of these cytochromes, especially CYP3A4, should be carefully monitored or avoided, whenever is possible (see [APPENDIX 3](#)).

A potentially significant interaction with aprepitant is suggested by available phase II data from ovarian cancer patients. Aprepitant use was forbidden in Cycle 1 in all patients. Four patients treated with aprepitant in Cycle 2 with available PK data had their PM01183 clearance reduced by 50%, approximately, compared to their Cycle 1 exposure. Clinically, some of these patients had unusually long-lasting neutropenia and/or severe thrombocytopenia during Cycle 2. Although all patients eventually recovered, the use of aprepitant is currently forbidden in the PM01183 treatment arms from all phase II/III PM01183 studies.

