APPENDIX 3: LIST OF CYP1/CYP2/CYP3 INHIBITORS, INDUCERS AND SUBSTRATES

Table 1. Classification of In Vivo Inhibitors of CYP Enzymes (1)

CYP enzymes	Strong Inhibitors (2) ≥ 5-fold increase in AUC or > 80% decrease in CL	Moderate inhibitors (3) ≥ 2 but < 5-fold increase in AUC or 50-80% decrease in CL	Weak inhibitors (4) ≥ 1.25 but < 2-fold increase in AUC or 20-50% decrease in CL
CYP1A2	Ciprofloxacin, enoxacin, fluvoxamine	Methoxsalen, mexiletine, oral contraceptives, phenylpropanolamine, thiabendazole, zileuton	Acyclovir, allopurinol, caffeine, cimetidine, Daidzein, (5), disulfiram, Echinacea, (5) famotidine, norfloxacin, propafenone, propranolol, terbinafine, ticlopidine, verapamil
CYP2B6			Clopidogrel, ticlopidine prasugrel
CYP2C8	Gemfibrozil(6)		Fluvoxamine, ketoconazole, trimethoprim
CYP2C9		Amiodarone, fluconazole, miconazole, oxandrolone	Capecitabine, cotrimoxazole, etravirine, fluvastatin, fluvoxamine, metronidazole, sulfapyrazone, tigecycline, voriconazole, zafirlukast
CYP2C19	Fluconazole, (7) Fluvoxamine, (8) ticlopidine (9)	Esomeprazole, fluoxetine, moclobemide, omeprazole, voriconazole	Allicin (garlic derivative), armodafinil, carbamazepine, cimetidine, etravirine, human growth hormone (rhGH), felbamate, ketoconazole, oral contraceptives (10)
CYP3A	Boceprevir, clarithromycin, conivaptan, grapefruit juice, (11) indinavir, itraconazole, ketoconazole, lopinavir/ritonavir, mibepradil, (12) nefazodone, neflifavir, posaconazole, ritonavir, saquinavir, telaprevir, telithromycin, voriconazole	Amprenavir, aprepitant, atazanavir, ciprofloxacin, darunavir/ritonavir, diltiazem, erythromycin, fluconazole, fosamprenavir, grapefruit juice, (11) imatinib, verapamil	Alprazolam, amiodarone, amlodipine, atorvastatin, bicalutamide, cilostazol, cimetidine, cyclosporine, fluoxetine, fluvoxamine, ginkgo, (5) goldenseal, (5) isoniazid, nilotinib, oral contraceptives, ranitidine, ranolazine, tipranavir/ritonavir, zileuton
CYP2D6	Bupropion, fluoxetine, paroxetine, quinidine	Cinacalcet, duloxetine, terbinafine	Amiodarone, celecoxib, cimetidine, desvenlafaxine, diltiazem, diphenhydramine, Echinacea, (5) escitalopram, febuxostat, gefitinib, hydralazine, hydroxychloroquine, imatinib, methadone, oral contraceptives, propafenone, ranitidine, ritonavir, sertraline, telithromycin, verapamil

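### Aprepitant, a moderate CYP3A inhibitor, is banned in Arm A, but strong CYP3A inhibitors are left to discretionary advice, so full-dose PM01183 with one complies with the protocol

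*Protocol*

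**What the plan says.** Section 6.7.2 prohibits aprepitant and its equivalents, such as fosaprepitant, for Arm A. No other CYP3A inhibitor is on that list.

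The reason is in Section 6.7.3. Four phase II patients given aprepitant in Cycle 2 "had their PM01183 clearance reduced by 50%, approximately, compared to their Cycle 1 exposure", and "some of these patients had unusually long-lasting neutropenia and/or severe thrombocytopenia during Cycle 2". The same section states, from work with human microsomes, that "CYP3A4 is the major CYP isoform involved in the metabolism of PM01183". For every other inhibitor or inducer of the relevant enzymes its advice, repeated in the synopsis, is that "concomitant drugs which induce or inhibit any of these cytochromes, especially CYP3A4, should be carefully monitored or avoided, whenever is possible". Section 6.7.3 then refers the reader to Appendix 3.

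Appendix 3, Table 1 grades the inhibitors. The moderate CYP3A cell begins "Amprenavir, aprepitant, atazanavir, ciprofloxacin, darunavir/ritonavir". The strong CYP3A cell begins "Boceprevir, clarithromycin, conivaptan, grapefruit juice, (11) indinavir, itraconazole, ketoconazole" and also includes posaconazole, telithromycin and voriconazole. The strong class is defined by "≥ 5-fold increase in AUC or > 80% decrease in CL". The appendix classifies drugs but attaches no ban, washout, hold or dose change to any class.

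**The concern.** The weaker inhibitor of the main metabolic route carries a firm prohibition, while the stronger ones are left to local judgement. The advice joins monitoring and avoidance with an 'or', so a site that gives the full dose alongside a strong inhibitor and watches the patient has followed the text. Section 5.2.2 defines a deviation as a departure from the protocol, so this need not be recorded as one.

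What monitoring would mean here is not specified. The routine schedule (Section 5.7, Table 6) has blood counts on Day 8 in Cycles 1 and 2, but from Cycle 3 only on Day 1. In the first-in-human study the nadir usually fell in the second week (Section 1.2.1.3). Primary CSF prophylaxis is also barred in Arm A unless the IDMC recommends it.

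At stake is avoidable myelosuppression in individual Arm A patients. Section 1.4 chose a dose 20% below the recommended dose for tolerability, and an unmanaged interaction can undo that choice.

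**Working it through.** **1. Which rule applies to which drug**

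| Place in protocol | Aprepitant | Strong CYP3A inhibitors |
|---|---|---|
| Appendix 3, Table 1 (CYP3A) | Moderate: 50-80% fall in clearance | Strong: more than 80% fall |
| 6.7.2 Prohibited | Banned in Arm A | Not listed |
| 6.4 Prophylactic medication | Banned with PM01183 | Not mentioned |
| 4.2 Exclusions | No rule on the drug | No rule on the drugs |
| 6.5, Table 8 | No item | No item |
| 6.6 Dose reduction | Only after toxicity or delay | Only after toxicity or delay |
| 6.7.3 and synopsis | Reason for the ban | Monitor or avoid |

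**2. Break-even for the dose margin**

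Inputs: recommended dose 4.0 mg/m², trial dose 3.2 mg/m² (Section 1.4). The plan's figure reproduces: 4.0 × (1 − 0.20) = 3.2.

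Take exposure as proportional to dose divided by clearance. A fractional fall x in clearance makes 3.2 mg/m² act like 3.2/(1 − x). Setting this equal to 4.0 gives x = 1 − 3.2/4.0 = 0.20. A 20% fall cancels the dose cut.

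**3. The aprepitant observation on the same scale**

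- With x = 0.50: 3.2/0.50 = 6.4 mg/m², and 6.4/4.0 = 1.6 times the recommended dose.
- Relative to break-even: 0.50/0.20 = 2.5.
- Dose that would restore the intended exposure: 3.2 × 0.50 = 1.6 mg/m², below the lowest permitted level of 2.0 mg/m² (Section 6.6, Table 11). The existing dose levels could not fully offset an interaction of that size, which favours avoidance or delay over a dose-reduction rule.

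**4. Can a strong inhibitor's effect be derived?**

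Write the fall in clearance as f × i, where f is the share of PM01183 clearance through CYP3A4 and i is the degree of inhibition. If aprepitant acted through CYP3A alone and within its Appendix 3 class (i from 0.50 to 0.80), a 50% fall requires f = 0.50/0.50 = 1.0 down to f = 0.50/0.80 = 0.625. Shares below about 63% do not fit the aprepitant result under that assumption. If aprepitant also acted in some other way, the result does not determine f. The documents give neither f nor any PM01183 data with a strong inhibitor, so the effect cannot be fixed from them.

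**5. How many patients could be exposed?**

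The strong CYP3A cell has 17 entries. Seven are HIV or hepatitis C antivirals (boceprevir, indinavir, lopinavir/ritonavir, nelfinavir, ritonavir, saquinavir, telaprevir), whose users are largely excluded by Section 4.2, items 1b and 1c. One (mibefradil) is footnoted as withdrawn in the United States. That leaves 17 − 7 − 1 = 9. Six of these are anti-infectives: clarithromycin, itraconazole, ketoconazole, posaconazole, telithromycin and voriconazole. Item 1d excludes active uncontrolled infection at entry, but not infection arising on treatment. The documents give no expected frequency of use.

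**The case against.** The asymmetry has an explanation. Aprepitant was banned because its effect on PM01183 was actually seen, and as an antiemetic it could accompany every cycle. Strong inhibitors have no PM01183 data and would be used rarely. The advice can also be read as preferring avoidance. This explains why aprepitant was listed. It does not explain why more potent inhibitors of the same pathway should stay discretionary.

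Safeguards exist, and they count. Table 8 requires ANC of at least 1.5 × 10⁹/l and platelets of at least 100 × 10⁹/l before each later dose. Grade 4 treatment-related events call for re-testing within 72 hours (Table 6). Febrile neutropenia is reported within 24 hours (Section 7.4.1). Neutropenia and thrombocytopenia are reviewed periodically (Section 7.5). All of these act after the exposure, and none prevents it.

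The evidence is thin: four patients, comparing Cycle 2 with Cycle 1, which the protocol itself presents as suggestive. Nor is reaching break-even harm in itself, because it returns the patient to the exposure of the recommended dose, where one of 15 patients had a dose-limiting toxicity (Section 1.2.1.3 of the protocol). Both points stand and limit the weight of the concern.

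A firmer rule for strong inhibitors would still leave moderate ones such as fluconazole, erythromycin and diltiazem under advice. That is a fair criticism. Banning the whole class would restrict many more drugs, and among moderate inhibitors the documents report PM01183 data only for aprepitant.

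Lastly, the Investigator's Brochure, to which Section 1.2.1 refers for full drug information, was not available. It may already contain a rule.

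**Conclusion.** The gap is real but modest. The protocol is not silent: it warns about CYP3A4 and points to a list. What is missing is a mandatory rule for strong CYP3A inhibitors, so full-dose PM01183 with one complies with the plan. A 20% fall in clearance would remove the dose margin, assuming exposure is proportional to dose over clearance. Few patients are likely to be affected.

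A reader might go further and apply the Appendix 3 threshold for strong inhibitors directly to PM01183: 3.2/(1 − 0.80) = 16 mg/m², four times the recommended dose. The documents do not support that. The threshold describes an inhibitor's effect on substrates of the enzyme. PM01183 is also metabolized by CYP2E1, CYP2D6 and CYP2C9 (Section 6.7.3), and the CYP3A4 share is not stated.

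A reader might also infer damage to the PFS comparison. Nothing here bears on the error rate or power of the primary analysis. This is a patient-safety improvement for Arm A.

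**What to change.** Add to Section 6.7.2 and the synopsis, for Arm A:

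> Strong CYP3A inhibitors (Appendix 3, Table 1) are prohibited during PM01183 treatment; use an alternative. If none is available, delay PM01183 until the inhibitor is stopped and washed out, within the limits of Section 6.5. Urgent treatment of infection is never withheld. If an inhibitor has to be started after an infusion, check blood counts at least weekly until recovery.

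The sponsor's clinical pharmacology group should set the washout interval, and the amendment should state it so that sites can apply the rule. Keep the aprepitant ban and the existing advice on all other inhibitors. If the Investigator's Brochure already sets a rule, use that one.

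The cost is a few sentences at the next amendment. Concomitant therapies are already collected from 14 days before the first infusion (Section 5.4, Table 5) and throughout treatment (Section 6.7). Grapefruit juice, which the table lists as both strong and moderate depending on the preparation, may not be captured as a treatment and is better handled by advice to patients. The downside is an occasional drug substitution, cycle delay or discontinuation in Arm A, plus some extra blood counts.

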6.8 DRUG ACCOUNTABILITY

Proper drug accountability will be done by the appropriate trained study personnel. Each study site will keep records to allow a comparison of quantities of drug received and used at each site for monitoring purposes. The Investigator at each study site will be the person ultimately responsible for drug accountability at the site.

All unused drug supplied by the Sponsor will be properly destroyed at the study site. Documentation of this procedure must be provided to the clinical trial monitor. If the Sponsor agrees, unused drug supplies may be returned to the drug repository.

6.9 TREATMENT COMPLIANCE

The Investigator is ultimately responsible for supervising compliance with the instructions described in this study protocol.

7. STUDY EVALUATIONS

7.1 EFFICACY

The primary aim of this clinical trial is to determine a difference in PFS between PM01183 and PLD or topotecan in platinum-resistant ovarian cancer patients. Secondary endpoints of efficacy include antitumor activity according to RECIST v.1.1.

Antitumor activity will be assessed using the RECIST v. 1.1 (see [APPENDIX 2](#)) and followed until disease progression (PD) by the appropriate method [computed tomography (CT) scan or magnetic resonance imaging (MRI) of the pelvis, abdomen and chest].

Irrespectively of treatment arm, radiological and clinical tumor assessment will be performed symmetrically at baseline and every eight weeks from randomization until evidence of PD. Patients who finish treatment without radiological PD will continue with the tumor assessments every eight weeks (\pm two weeks) from randomization until PD, start of a new antitumor therapy, death or date of study termination (clinical cutoff), whichever occurs first.

After radiological PD is documented or a new antitumor therapy is started, patients will be followed for survival at least every three months (\pm two weeks) from the end-of-treatment visit until death or date of study termination, whichever occurs first. Once the whole recruitment is completed, the 3-month follow-up for patients who discontinue treatment due to PD will be performed according to a calendar time. Follow-up for survival, after radiological PD is documented or new therapy is started, may be made by telephone calls to the investigational sites.

The date of clinical and/or radiological PD and the date of death will be registered and documented as appropriate.

Copies of CT scans, MRIs and any other documented means to evaluate tumor response or progression should be available for external radiological review by an IRC. The IRC will determine the patient's best response and assign the date of objective response or progression/censoring according to RECIST v.1.1.

A futility analysis is planned when 210 patients are recruited (~105 patients enrolled in each arm). The IDMC will review the efficacy and safety data available at that time and, based on the observed results, might recommend stopping the trial; no claim for superiority in efficacy *vs.* the control arm is foreseen at that time.

7.2 SAFETY

Patients will be evaluable for safety if they have received any partial or complete treatment infusion. All AEs will be graded according to the NCI-CTCAE v.4. Treatment delays, dose reduction requirements and reason for treatment discontinuation will be monitored throughout the study.

The safety profile of patients will be monitored throughout the treatment and up to 30 days after the last treatment infusion (end of treatment, EOT), or until the patient starts a new antitumor therapy or until the date of death, whichever occurs first.

Any treatment-related AEs will be followed until recovery to at least grade 1 or stabilization of symptoms, whichever occurs first.

An interim safety analysis will be performed by the IDMC after the recruitment of the first 40 patients in the PM01183 arm (Arm A) to assess if the addition of primary CSF prophylaxis might be necessary. Although febrile neutropenia did not occur in the first-in-human PM01183 single-agent study, based on pooled data available from all ongoing phase II studies at 7.0 mg FD, it occurred in about 16% of patients. In this clinical trial, the expected percentage of febrile neutropenia is lower, as the PM01183 dose will be administered based on BSA and at a dose (3.2 mg/m²) below the RD found in the first-in-human PM01183 trial (4.0 mg/m² = 7.0 mg FD).

Furthermore, PM01183, PLD and topotecan dose will be capped at a BSA of 2.0 m² in those patients who have a greater BSA.

At the time of the interim safety analysis, recruitment in the control arm (Arm B, PLD and topotecan) is also expected to be 40 patients.

Safety evaluations will be also performed by the IDMC during the futility analysis to be conducted in all treatment arms once 210 patients are recruited.

7.3 ADVERSE EVENTS DEFINITIONS

7.3.1 Adverse Event (AE)

An AE is any untoward medical occurrence in a patient or clinical investigation patient administered a pharmaceutical product which does not necessarily have a causal relationship with this treatment.

An AE can therefore be any unfavorable and unintended sign, (e.g., an abnormal laboratory finding), or a disease temporally associated with the use of a medicinal product, whether or not considered related to the medicinal product.

Illnesses with onset during the study or exacerbations of pre-existing illnesses, including but not limited to clinically significant changes in physical examination findings and abnormal objective tests/procedures findings (e.g., X-ray, ECG) should be recorded. The criteria for determining whether an abnormal objective test finding should be reported as an AE are as follows:

- The test result is associated with clinically significant symptoms, and/or
- The test result leads to a change in the study dosing or discontinuation from the clinical trial, significant additional concomitant drug treatment or other therapy, and/or
- The test result leads to any of the outcomes included in the definition of a SAE (see definition below), and/or
- The test result is considered to be clinically relevant by the Investigator.

“Disease progression” will not be reported as an AE, as this information will be used for efficacy assessment.

7.3.2 Serious Adverse Event (SAE)

A SAE is any adverse experience occurring at any dose that:

- Results in death (is fatal),
- Is life-threatening,
- Requires or prolongs inpatient hospitalization,
- Results in persistent or significant disability or incapacity,
- Is a congenital anomaly or birth defect,
- Is medically significant, or
- Is any suspected transmission of an infectious agent via a medicinal product.

Medical and scientific judgment should be exercised in deciding medically significant events; this criterion should be applied to AEs that may not be immediately life-threatening or result in hospitalization but may jeopardize the patient or may require intervention to prevent one of the outcomes listed in the above definition.

“Disease progression” as a term will not be reported as a SAE.

7.3.3 Death

Death as such is the outcome of a SAE and should not be used as the SAE term itself. The cause of death should be recorded as the SAE term instead. When available, the autopsy report will be provided to the Sponsor.

Grade 5 should be used for events which lead immediately (within 24 hours) and directly to death, and grade 4 should be used with outcome death for events which lead to death after a longer time period, and that may also be linked to additional morbidities.

